6. GENERAL STATISTICAL CONSIDERATIONS

6.1. General Principles

All continuous variables, unless otherwise specified, will be summarized using the following descriptive statistics: n (non-missing sample size), mean, standard deviation, median, minimum and maximum. Titers will be summarized with geometric means, first across replicates to compute one value for each individual sample and then across subjects within a study group. Percentages of cell types will also be summarized by geometric means within each study group. The frequency and percentages (based on the non-missing sample size) of observed levels will be reported for all categorical measures. In general, all data will be listed, sorted by treatment and subject, and when appropriate by visit number within subject. All summary tables will be structured with a column for each vaccination group in the order presented in Table 1 and will be annotated with the total population size relevant to that table/treatment, including any missing observations.

If a substantial number of subjects meet eligibility criteria, but had intercurrent infections that might affect the immunoassay results for the vaccine strains, sensitivity analyses will be performed excluding those and qualitative comparisons will be made with the mITT and PP analyses.

6.2. Timing of Analyses

No interim analysis is planned.

The final analysis will be performed after the last subject completes the final visit, and the database is cleaned, monitored, and locked. A topline report will be generated upon receipt and processing of immunogenicity data (T cell responses after stimulation with M-001 peptides and with other Influenza A antigens, and M-001 ELISA responses) through Day 200. Tables and figures to be included have an asterisk following the title.

The CSR will be completed when all primary and secondary endpoint data are available. All available exploratory endpoint data will be included in the CSR, and additional data not available at the time of CSR generation will be included in one or more addendums, depending on the timing of each set of exploratory assays.

6.3. Analysis Populations

A tabular listing of all subjects, visits, and observations excluded from the analysis populations will be provided in Listing 5. In the case of mis-randomization, subjects will be analyzed according to the study product actually received for all analysis populations.

6.3.1. Modified Intent-to-Treat (mITT) Population

The modified intent-to-treat (mITT) population includes all subjects who received at least one dose of study vaccine and contributed at least one post-study vaccination venous blood sample for immunogenicity testing for which valid results were reported.

6.3.2. Per Protocol Population

The per protocol (PP) population includes all subjects in the mITT subset with the following exclusions:

- Data from all available visits for subjects found to be ineligible at baseline
- Data from all visits subsequent to major protocol deviations, such as:
 - Second or third study vaccination not received

- Second or third study vaccination received out of window
- Receipt of non-study licensed live vaccine within 30 days before or 21 days after each study vaccination
- Receipt of non-study licensed inactivated vaccine within 14 days before or 21 days after each study vaccination
- Receipt of non-study seasonal influenza vaccine (live or inactivated) within 30 days before or for the duration of the study
- o Receipt of immunosuppressive therapy (e.g., corticosteroids) within 30 days before or after each of the first two study vaccinations (Dose 1 and Dose 2)
- Data from any visit that occurs out of window
 - O Visit 03: Day 14 + 2 days post vaccination 1
 - O Visit 04: Day 22 + 2 days post vaccination 1
 - Visit 06: Day 14 + 2 days post vaccination 2
 - Visit 07: Day 21 + 7 days post vaccination 2
 - Visit 08: Day 56 + 7 days post vaccination 2
 - O Visit 09: Day 150 ± 30 days post vaccination 2
 - O Visit 10: Day 14 + 3 days post vaccination 3
 - O Visit 11: Day 28 + 7 days post vaccination 3

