7.2. Follow-up

7.2.1. Visit 2, Day 9, Clinic Visit (8 days [+2 days] post first study vaccination)

- Study personnel will review the Memory Aid information with subjects and assess and record all AE/SAEs and concomitant medications on the appropriate data collection form.
- Counsel women of childbearing potential on contraception and avoidance of pregnancy.
- If indicated by review of Memory Aid, obtain vital signs.
- A targeted physical examination may be performed by a study clinician licensed to make medical diagnoses and listed on the Form FDA 1572 as the site PI or sub-I, if indicated based on review of interim medical history.
- Examine the vaccination site for Dose 1.
- Approximately 10 mL of venous blood will be collected for safety labs.

7.2.2. Visit 3, Day 15, Clinic Visit (14 days [+2 days] post first study vaccination)

- Study personnel will review interim medical history with subjects and assess and record all AE/SAEs and concomitant medications on the appropriate data collection form.
- Counsel women of childbearing potential on contraception and avoidance of pregnancy.
- If indicated, obtain vital signs.
- A targeted physical examination may be performed by a study clinician licensed to make medical diagnoses and listed on the Form FDA 1572 as the site PI or sub-I, if indicated based on review of interim medical history.
- Approximately 40 mL of venous blood will be collected for isolation of PBMCs.

7.2.3. Visit 4, Day 22, Dose 2, Clinic Visit (21 days [+2 days] post first study vaccination)

- Eligibility criteria will be reviewed with subjects prior to the second study vaccination to assure continued eligibility.
- Obtain interim medical history by interview of subjects prior to the second study vaccination and note any changes since the previous visit.
- All concomitant medications will be recorded on the appropriate data collection form prior to the second study vaccination.
- All AE/SAEs will be assessed and recorded on the appropriate data collection form prior to the second study vaccination.
- Vital signs, including oral temperature, pulse, and blood pressure, will be obtained prior to the second study vaccination. Subjects must not eat or drink anything hot or cold, or smoke within 10 minutes prior to taking oral temperature.

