4.4.5. Selection and Timing of Dose for Each Subject

All subjects receive the assigned vaccination at Day 1 and Day 22 (+2 days), followed by a single dose of IIV4 on approximately Day 172 (±30 days).

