9.5.1 Efficacy/Immunogenicity and Safety Measurements Assessed and Flow Chart

Table 2: Schedule of Study Procedures

Study Visit (V)	01	02	03	04	05	06	07	08	09	10	11	12
Study Day	1	9	15	22	30	36	43	78	172	186	200	200 ⁺
Visit Windows		(+2)	(+2)	(+2)	(+2)	(+2)	(+7)	(+7)	142-202	(+3)	(+7)	(+14)
Sign Consent Form ¹	X											
Assess eligibility	X			X					X			
Collect demographic information	X											
Review Medical History	X		X	X		X	X	X	X	X	X	X
Concomitant meds	X	X	X	X	X	X	X	X^7	X^7	X^7	X ⁷	X^7
Vital signs ²	X	{X}	{X}	X	{X}	{X}	{X}	{X}	X	{X}	{X}	
Height, Weight	X											
Targeted Physical Exam	{X}	{X}	{X}	{X}	{X}	{X}	{X}	{X}	{X}	{X}	{X}	
Review contraception/ Counseling ³	X	X	X	X	X	X	X	X	X	X		
Pregnancy Test ^{2,4}	X			X					X			
Blood - Safety Labs (10 mL)	X	X			X							
Blood – Antibody Assays (10-20 mL)	X			X			X	X	X*		X*	
Blood – PBMCs (40-60 mL)	X=		X			X	X=	X	X	X	X	
Randomization	X											
AE/SAE Assessment ^{2#}	X	X	X	X	X	X	X	X	X	X	X	X
Vaccination ⁴	X ⁵			X ⁵					X			
Evaluate vaccination site	X	X		X	X							
Postvaccination procedures ⁶	X			X								
Review Memory Aid Data		X			X							
Blood volume (mL)	80	10	40	10	10	40	70	50	60	40	60	
required at this visit only if clinically indica	atad						•					

^{ } required at this visit only if clinically indicated

Consent process completed and form signed before any study-related procedures are conducted.

Vital signs include blood pressure, pulse, and oral temperature. On vaccination visits, these items should be completed prior to vaccination.

Counseling on avoidance of pregnancy for women of childbearing potential.

Urine or serum pregnancy test must be negative and be completed within 24 hours prior to vaccination for women of childbearing potential.

All subjects will be observed for a minimum of 20 minutes following vaccination.

⁶Post-vaccination procedures will include documentation of any reactogenicity during the observation period and any AEs/SAEs post-vaccination, as well as provision of Memory Aid and instructions on completion.

⁷ Concomitant medications (vaccines only) will be recorded on the appropriate data collection form after Visit 7 through the end of the study.

*Visit 12 will occur as a phone call only if visit 11 occurs prior to Study Day 200.

*20 mL of blood will be collected for antibody assays on these days; 10 mL will be collected on other days of collection for antibody assays

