14.1 Description of Study Subjects

14.1.1 Disposition of Subjects

Table 13: Subject Disposition by Study Arm

Subject	_	1 mg M-001 N=X)	-	B: Placebo =X)	All Su (N=	
Disposition	n	%	n	%	n	%
Screened					х	
Enrolled/Randomized	Х	100	х	100	х	100
Received Study Vaccination	Х	XX	х	XX	х	xx
Received first 2 doses	Х	XX	х	XX	х	xx
Received All Scheduled Study Vaccinations ^a	Х	XX	х	XX	х	xx
Completed PBMC Blood Draw at Study Day 43 (Visit 07)	х	xx	x	xx	х	XX
Completed Follow-up (Study Day 200) ^a	Х	XX	x	xx	х	xx
Completed Final PBMC Blood Draw (Day 200 / Visit 11)	X	XX	x	xx	X	xx

Note: N=Number of subjects enrolled.

^a Refer to Listing 2 for reasons subjects discontinued or terminated early.

Table 14: Analysis Populations by Study Arm

		Grou 1 mg l (N=	M-001	Plac	ip B: cebo =X)	All Su (N=	
Analysis Populations	Reason Subjects Excluded	n	%	n	%	%	n
Safety Analysis Population	Any Reason	х	xx	X	xx	х	xx
	No Study Vaccination Received						
Modified Intent-to-Treat Population	Any Reason						
	No Study Vaccination Received						
	Ineligible at Baseline						
	No Post-Vaccination Results Available						
Per Protocol, Day 9	Any Reason						
	No Study Vaccination Received						
	Ineligible at Baseline						
	No Day 9 Result Reported by Lab						
	Receipt of Non-Study Vaccination						
	Receipt of Immunosuppressive Medication						
	Day 9 Visit Out of Window						
Per Protocol, Day 15	Any Reason						
	No Study Vaccination Received						
	Ineligible at Baseline						
	No Day 15 Result Reported by Lab						
	Receipt of Non-Study Vaccination						
	Receipt of Immunosuppressive Medication						
	Day 15 Visit Out of Window						
Per Protocol, Day 22	Any Reason						
	No Study Vaccination Received						
	Ineligible at Baseline						
	No Day 22 Result Reported by Lab						
	Receipt of Non-Study Vaccination						
	Receipt of Immunosuppressive Medication						
	Day 22 Visit Out of Window						
Per Protocol, Day 30	Any Reason						
	No Study Vaccination Received						
	Study Vaccination 2 Not Received						
	Study Vaccination 2 Out of Window						
	Ineligible at Baseline						
	No Day 30 Result Reported by Lab						
	Receipt of Non-Study Vaccination						

Table 14: Analysis Populations by Study Arm (Continued)

		Grou 1 mg N (N=	M-001	Group B: Placebo (N=X)		All Subjects (N=X)	
Analysis Populations	Reason Subjects Excluded	n	%	n	%	%	n
	Receipt of Immunosuppressive Medication						
	Day 30 Visit Out of Window						
Per Protocol, Day 36 (Primary Endpoint)	Any Reason						

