	No Study Vaccination Received						
	Study Vaccination 2 Not Received						
	Study Vaccination 2 Out of Window						
	Ineligible at Baseline						
	No Day 36 Result Reported by Lab						
	Receipt of Non-Study Vaccination						
	Receipt of Immunosuppressive Medication						
	Day 36 Visit Out of Window						
Per Protocol, Day 43	Any Reason						
	No Study Vaccination Received						
	Study Vaccination 2 Not Received						
	Study Vaccination 2 Out of Window						
	Ineligible at Baseline						
	No Day 43 Result Reported by Lab						
	Receipt of Non-Study Vaccination						
	Receipt of Immunosuppressive Medication						
	Day 43 Visit Out of Window						
Per Protocol, Day 78	Any Reason						
	No Study Vaccination Received						
	Study Vaccination 2 Not Received						
	Study Vaccination 2 Out of Window						
	Ineligible at Baseline						
	No Day 78 Result Reported by Lab						
	Receipt of Non-Study Vaccination						
	Receipt of Immunosuppressive Medication						
	Day 78 Visit Out of Window						
Per Protocol, Day 172	Any Reason						
	No Study Vaccination Received						
	Study Vaccination 2 Not Received						
	Study Vaccination 2 Out of Window						

Table 14: Analysis Populations by Study Arm (Continued)

		Group A: 1 mg M-001 (N=X)		Group B: Placebo (N=X)		All Subjects (N=X)	
Analysis Populations	Reason Subjects Excluded	n	%	n	%	%	n
	Ineligible at Baseline						
	No Day 172 Result Reported by Lab						
	Receipt of Non-Study Vaccination						
	Receipt of Immunosuppressive Medication						
	Day 172 Visit Out of Window						
Per Protocol, Day 186	Any Reason						
	No Study Vaccination Received						
	Study Vaccination 3 Not Received						
	Study Vaccination 3 Out of Window						
	Study Vaccination 2 Not Received						
	Study Vaccination 2 Out of Window						
	Ineligible at Baseline						
	No Day 186 Result Reported by Lab						
	Receipt of Non-Study Vaccination						
	Receipt of Immunosuppressive Medication						
	Day 186 Visit Out of Window						
Per Protocol, Day 200	Any Reason						
	No Study Vaccination Received						
	Study Vaccination 3 Not Received						
	Study Vaccination 3 Out of Window						
	Study Vaccination 2 Not Received						
	Study Vaccination 2 Out of Window						
	Ineligible at Baseline						
	No Day 200 Result Reported by Lab						
	Receipt of Non-Study Vaccination						
	Receipt of Immunosuppressive Medication						
	Day 200 Visit Out of Window						

Table 15: Dates of First Vaccination by Site and Study Arm

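### The SAP's per-protocol window for Visit 04 runs one day late (22 to 24 days after Dose 1, against 21 to 23 elsewhere), so read literally it drops Day 22 antibody data from subjects seen on the scheduled day.

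*SAP*

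**What the plan says.** SAP 6.3.2 has two timing exclusions from the per-protocol population. One works at visit level: "Data from any visit that occurs out of window". Under it the SAP lists eight visit windows, and the entry for the Dose 2 visit is "Visit 04: Day 22 + 2 days post vaccination 1". The other works at dose level, "Second or third study vaccination received out of window", and removes all later visits. No number of days is attached to it in that section.

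Three other places give the timing of this visit:

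- Protocol 7.2.3: "Visit 4, Day 22, Dose 2, Clinic Visit (21 days [+2 days] post first study vaccination".
- SAP 4.4.5: "All subjects receive the assigned vaccination at Day 1 and Day 22 (+2 days".
- SAP Table 2 ("Table 2: Schedule of Study Procedures"): Visit 04 at study day 22 with a window of +2.

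SAP 4.4.3 also puts the two priming doses 21 days apart.

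SAP 8 bases all immune-response analyses on the per-protocol population and adds the mITT population only as a sensitivity analysis of the primary endpoint. SAP 12 confirms that the mITT analyses of antibody responses were dropped.

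**The concern.** The protocol window runs forward only (+2, with no minus), so the scheduled day is also the earliest permitted day. A per-protocol window that starts one day later removes the subjects who attended exactly on time. It also admits a visit one day beyond the protocol's limit.

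Visit 04 draws antibody serum and no PBMCs (SAP Table 2). Day 22 is a planned M-001 ELISA time point for both seroconversion and GMT (SAP 8.3, Table 44). With no mITT antibody analysis, no second analysis would retain the excluded samples.

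There is also a secondary risk. Visit 04 is the visit at which Dose 2 is given, and 6.3.2 supplies no other number for its dose-level flag. If a programmer reused the Visit 04 line for that flag, every later per-protocol visit, including the Day 36 primary endpoint, would be lost for subjects dosed on the scheduled day.

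**Working it through.** **Inputs.** Scheduled study days come from SAP Table 2. The doses fall on study days 1, 22 and 172 (SAP Table 1). The nominal days come from the list in SAP 6.3.2.

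**Step 1: which scale does the list use?** Days after dose = scheduled study day − study day of the reference dose.

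| Visit | Study day − dose day | Result | SAP 6.3.2 | Agrees |
|---|---|---|---|---|
| 03 | 15 − 1 | 14 | 14 | yes |
| 04 | 22 − 1 | 21 | 22 | **no** |
| 06 | 36 − 22 | 14 | 14 | yes |
| 07 | 43 − 22 | 21 | 21 | yes |
| 08 | 78 − 22 | 56 | 56 | yes |
| 09 | 172 − 22 | 150 | 150 | yes |
| 10 | 186 − 172 | 14 | 14 | yes |
| 11 | 200 − 172 | 28 | 28 | yes |

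Seven of eight lines count days since the dose and reproduce exactly. Visit 03, directly above Visit 04 and tied to the same dose, is one of them: study day 15 is written as day 14.

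**Step 2: compare the windows.**

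- Protocol 7.2.3: 21 + {0, 1, 2} = {21, 22, 23} days after Dose 1, which is study days 22 to 24. SAP 4.4.5 and SAP Table 2 give the same study days.
- SAP 6.3.2 as written: 22 + {0, 1, 2} = {22, 23, 24} days after Dose 1, which is study days 23 to 25.
- In both: {22, 23}. Excluded although on schedule: {21}. Accepted although outside the protocol window: {24}.

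**Step 3: try the benign reading.** If 22 is taken as a study day, the window becomes study days 22 to 24 and the conflict disappears. That reading goes against the line's own statement that it counts from vaccination 1, and against the other seven lines.

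**Step 4: size.** The loss is the share of subjects seen at exactly 21 days. The documents do not give it, so it could be anything from 0% to 100% of the Day 22 per-protocol data. Two assumed shares illustrate the effect on the plan's own precision measure, the exact (Clopper-Pearson) 95% interval at an observed 50%:

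- No loss, n = 60 per arm: (36.8, 63.2), which reproduces SAP Table 4.
- One third lost, n = 60 × 2/3 = 40: (33.8, 66.2).
- One half lost, n = 60 × 1/2 = 30: (31.3, 68.7).

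The interval width goes from 26.4 points (63.2 − 36.8) to 32.4 (66.2 − 33.8) or 37.4 (68.7 − 31.3).

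**The case against.** The strongest reply is that this is a label carried over by mistake. Study day 22 is how the SAP names this visit in 4.4.5, Table 2 and Table 14, and a programmer who read it that way would exclude nobody wrongly. That explanation of the origin is probably right, but the text does not support reading the line that way, and an exclusion rule should not depend on a guess.

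A second reply is that a wrong exclusion would show. Table 14 counts "Day 22 Visit Out of Window" by arm, Listing 5 records each exclusion and whether available results were removed, and Listing 16 shows ELISA results by actual study day. This makes the error likely to be noticed, but only after the flags have been programmed.

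Third, the reach is limited. The ELISA measure is exploratory, Table 44 carries no test, and the assay is also reported at Days 43, 78, 172 and 200. This stands. The Table 30 mock-up has a Day 22 HAI block, but the outcome list in SAP 3.2.2 plans HAI and neutralization on Days 1, 43, 172 and 200 only, so that block adds little weight.

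Fourth, spillover to Dose 2 is not established. Table 14 lists "Study Vaccination 2 Out of Window" as a separate reason, SAP 4.4.5 gives a dosing window that agrees with the protocol, SAP 7.2 provides for review before exclusion, and the mITT analysis keeps these subjects for the primary endpoint. This also stands: it is a risk created by a missing definition, not a predicted result.

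Finally, the one-third and one-half shares have no source in the documents, and a start of 60 per arm ignores the plan's allowance of up to 5% per-protocol exclusions, which it states for the primary immunogenicity outcome. The intervals are illustrations only.

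**Conclusion.** The concern holds: the Visit 04 line in SAP 6.3.2 is wrong as written. It conflicts with protocol 7.2.3 and with SAP 4.4.3, 4.4.5 and Table 2, and it breaks the convention of the seven other lines in its own list. The one-day shift is certain; the data loss depends on the line being applied literally.

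If it is, the direct effect falls on the Day 22 per-protocol antibody data, chiefly the exploratory M-001 ELISA. The size lies between 0% and 100% of those data and cannot be narrowed from the documents. No effect on the Day 36 primary endpoint is claimed. The point should be settled because the conflict sits in an operative exclusion rule, the antibody analyses have no fallback population, and the correction costs almost nothing.

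**What to change.** Before the per-protocol flags are programmed, reconcile the Visit 04 analysis window in SAP 6.3.2 with protocol 7.2.3, SAP 4.4.5 and SAP Table 2, and express it in days after vaccination like the other seven lines. Add one sentence to 6.3.2 stating that the flag for a second vaccination received out of window uses that reconciled window.

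The cost is one corrected line and one added sentence. No new data are needed.

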6.3.3. Safety Analysis Population

The Safety Analysis population includes all subjects who received at least one dose of study vaccine.

6.4. Covariates and Subgroups

The protocol does not define any formal subgroup analyses, and the study is not adequately powered to perform subgroup analyses.

6.5. Missing Data

All attempts will be made to collect all data per protocol. As missing data are expected to be minimal, no imputation will be performed for missing values. Any data point that appears to be erroneous or inexplicable based on clinical judgement will be investigated as a possible outlier. If data points are identified as outliers, sensitivity analyses will be performed to examine the impact of including or excluding the outliers. Any substantive differences in these analyses will be reported.

6.6. Interim Analyses and Data Monitoring

Interim safety data is reviewed by the DSMB as described in Protocol Section 9.6.2. Interim summary reports for the DSMB safety review include enrollment and demographic information, medical history, concomitant medications, physical assessments, clinical laboratory values, solicited reactogenicity events and unsolicited AE/SAEs. There were no formal interim analyses planned.

6.7. Multicenter Studies

Data will be pooled across all three clinical sites. Center effects are not anticipated because the sites are using standardized procedures for vaccination and assessment of solicited and unsolicited adverse events, and the study relies on central laboratories for the assessment of immunogenicity endpoints.

6.8. Multiple Comparisons/Multiplicity

While there will be multiple comparisons performed for the primary immunogenicity objective (for each of five parameters alone measured in CD4 and CD8 T cells plus any combinations measures), it is assumed that these analyses are not intended to be confirmatory and thus no adjustment for multiple comparisons is considered

7. STUDY SUBJECTS

7.1. Disposition of Subjects

The disposition of subjects in the study will be tabulated by study arm (Table 13). The table shows the total number of subjects screened, enrolled, received treatment, received all treatment, completed follow-up, completed the final blood draw, and the number completing the study. The composition of analysis populations, including reasons for subject exclusion is presented by study arm in Table 14. The dates of each study vaccination will be summarized by site and study arm in Table 15, and a summary of screening failures will be presented in Table 16.

A flowchart showing the disposition of study subjects, adapted from the Consort Statement [11] will be included (Figure 1). This figure will present the number of subjects screened, enrolled, lost to follow-up, and analyzed, by study arm.

A listing of subjects who discontinued dosing or terminated from study follow-up and the reason will be included in Listing 2. A listing of all subjects receiving investigational product will be given in Listing 1.

